13.2 Solicited Local and Systemic Adverse Events

For details please refer to [section 7.1.1 of the protocol](#).

Only solicited local and systemic adverse events reported in the diary card will be analyzed. Implausible measurements will not be taken into consideration in the analysis but listed in the Appendix.

Solicited adverse events will be reported at 30 minutes, at approximately 6 hours post-vaccination on day 1 and then daily until day 7 using structured diaries. The analyses of solicited adverse events will be done separately for 30 minutes and based on three intervals: 6h - day 3, day 4 - 7 and 6h - day 7, each without 30 minutes data. In addition solicited adverse events ongoing after day 7 will be presented as unsolicited AEs.

For erythema, induration and swelling recorded originally as diameters (mm), the following categorization will be used to summarize the data:

Grade 0 (< 25 mm), any (25-50 mm, 51-100 mm, >100 mm)

Body temperature will be broken down by route of measurement according to the recommendations of the Brighton collaboration and will be summarized according to the 3 schemes described below:

- by 0.5 °C increments: <36.0, ≥36.0-<36.5, ≥36.5-<37.0, ≥37.0-<37.5, ≥37.5-<38.0, ≥38.0-<38.5, ≥38.5-<39.0, ≥39.0-<39.5, ≥39.5-<40.0, ≥40.0°C
- by 1.0 °C increments: <36.0, ≥36.0-<37.0, ≥37.0-<38.0, ≥ 38.0-<39.0, ≥39.0-<40, ≥40°C
- <38.0, ≥38.0 °C

Fever, defined as a body temperature of ≥38°C irrespective of route of measurement, will be integrated to the summaries as an indicator of a systemic adverse event.

The analyses will encompass summaries of the data on five levels:

1. Daily reports of subjects with solicited adverse events.
2. Time of first onset of solicited adverse events (excluding 30 min measurement).
3. Solicited adverse events, maximum event severity by event and interval (6h - day 3, day 4 -7, and 6h - day 7, each without 30 min).
4. Duration of solicited adverse events.
5. Solicited adverse events and indicators of solicited adverse events, occurrence of at least one event by category (local, systemic) and interval (6h-Day 3, Day 4-7 and 6h-Day 7, each without 30 min).

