For each of the time points or time intervals presented in the summaries, only subjects with at least one plausible observation (i.e., any non-missing values but excluding “Not done/unknown” and implausible values) for the solicited adverse events in the interval of interest will be considered. Subjects without plausible data (i.e. missing values or reported as “Not done/unknown” and implausible values) will be removed from the denominator to prevent a downward bias (towards zero).

Level 1: Daily reports of solicited adverse event

For each of the time points only subjects with at least one plausible observation (i.e., any non-missing values but excluding “Not done/unknown” and implausible values) for the solicited adverse event in the interval of interest will be considered. Subjects without plausible data (i.e. missing values or reported as “Not done/unknown” and implausible values) will be removed from the denominator in order to prevent a downward bias (towards zero). Data collected will be summarized (frequencies and percentages of subjects) by vaccine group, solicited adverse event, vaccination number and time point.

Level 2: Time of first onset of solicited adverse events

The **time of first onset** is defined, for each subject, for each solicited adverse event, as the time point at which the respective solicited adverse event first occurred. For erythema, induration and swelling the following threshold will be used ≥ 25 mm. The summary will provide the frequencies and percentages of subjects with first onset of each solicited adverse events by vaccine group, by vaccination number, and by each time point.

The tables below show examples of a listing considering four subjects who receive two vaccinations, with post-vaccination data for a given solicited adverse event and a summary table by vaccination group.

Table 13.2-1: Example for Time to First Onset of Solicited Adverse Events

Vaccination	Subject Number	6 Hours	Day 2	Day 3	Day 4	...	Day 7
1	PP D	None	Severe	Moderate	None	...	None
	PP D	Mild	None	None	Moderate	...	Missing
	PP D	Moderate	Mild	None	Severe	...	Mild
	PP D	Mild	Mild	None	None	...	None
2	PP D	None	None	None	None	...	Not done
	PP D	None	Mild	Mild	Missing	...	Missing
	PP D	Severe	None	Mild	Missing	...	None
	PP D	Missing	Missing	Missing	Severe	...	Mild

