For each vaccination the first onset of the adverse event will be used for each subject. For any vaccination the worst adverse event across all vaccinations per time point will be used. Note, ‘not done’ is treated identical to ‘missing’.

Table 13.2-2: Time to First Onset of Solicited Adverse Events

Vaccine group A

Vaccination	Adverse event	Number (%) of Subjects						...	DAY 7 (N=4)
		6 HRS (N=4)	DAY 2 (N=4)	DAY 3 (N=4)	DAY 4 (N=4)				
1	XY	n	4	4	4	4	...	3	
		ANY	3 (75.0%)	1 (25.0%)	0 (0%)	0 (0%)	...	0 (0%)	
		Mild	2 (50.0%)	0 (0%)	0 (0%)	0 (0%)	...	0 (0%)	
		Moderate	1 (25.0%)	0 (0%)	0 (0%)	0 (0%)	...	0 (0%)	
		Severe	0 (0%)	1 (25.0%)	0 (0%)	0 (0%)	...	0 (0%)	
2	XY	n	3	3	3	2	...	2	
		ANY	1 (33.3%)	1 (33.3%)	0 (0%)	1 (50.0%)	...	0 (0%)	
		Mild	0 (0%)	1 (33.3%)	0 (0%)	0 (0%)	...	0 (0%)	
		Moderate	0 (0%)	0 (0%)	0 (0%)	0 (0%)	...	0 (0%)	
		Severe	1 (33.3%)	0 (0%)	0 (0%)	1 (50.0%)	...	0 (0%)	
ANY	XY	n	4	4	4	4	...	3	
		ANY	3 (75.0%)	1 (25.0%)	0 (0%)	0 (0%)	...	0 (0%)	
		Mild	2 (50.0%)	0 (0%)	0 (0%)	0 (0%)	...	0 (0%)	
		Moderate	0 (0%)	0 (0%)	0 (0%)	0 (0%)	...	0 (0%)	
		Severe	1 (25.0%)	1 (25.0%)	0 (0%)	0 (0%)	...	0 (0%)	

N: no. of subjects with data at a time point across all vaccinations.

n: no. of subjects with data at a time point for that specific vaccination.

Level 3: Solicited adverse events, maximum event severity by event and interval

The **maximum event severity** will be defined if there is at least one plausible non-missing observation (excluding “Not done/unknown” and implausible values) within this time interval. Each subject’s data will be aggregated across the time points of the interval and summarized according to the maximal severity observed for each adverse event, followed by a summary across subjects for each vaccine. Subjects without any solicited adverse events in the interval, i.e., missing values at each of the requested time points,

will be removed from the denominator. Data collected will be summarized (frequencies and percentages of subjects) by vaccine group, solicited adverse event, vaccination number and time point.

Level 4: Number of days with solicited adverse events

The number of days with the adverse event is defined irrespective of severity. This means at least ‘mild’ solicited adverse event that are assessed qualitatively and ≥ 25 mm for erythema, induration and swelling. If a solicited adverse event continues beyond day 7 the period after day 7 is added.

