The following example is used to illustrate how the duration is calculated:

Suppose six subjects, who received a vaccination have the post-vaccination solicited adverse event data shown in the table below. In addition, there are unsolicited adverse event reports indicating that the adverse event in subject ^{PPD} and ^{PPD} continued until day 12 and day 8, respectively. For subject ^{PPD} the number of days is calculated as 6+5 and for subject ^{PPD} as 3+1. Missing values (‘Missing’) are not taken into consideration

Table 13.2-3: Example for Number of Days With Solicited Adverse Events

Subject Number	6 Hours	Day 2	Day 3	Day 4	Day 5	Day 6	Day 7	No. of days
^{PPD}	None	Severe	Moderate	None	None	None	None	2
^{PPD}	Mild	None	None	Moderate	Moderate	Moderate	Missing	4
^{PPD}	Moderate	Mild	None	Severe	Severe	Severe	Mild ^a	11
^{PPD}	None	None	None	None	None	None	Not done	0
^{PPD}	None	Mild	Mild	Missing	Missing	Missing	Missing	2
^{PPD}	Severe	None	Mild	None	None	None	Severe ^b	4

^a continued until day 12; ^b continued until day 8

The frequency distribution of the number of days will be provided in a summary table by vaccine group, vaccination number, and by solicited adverse event.

Level 5: Solicited adverse events, occurrence of at least one event by category (local, systemic) and interval.

The **occurrence of at least one solicited adverse event** is defined as “any” for a subject if he/she reports greater than “none” ≥ 25 mm, for erythema, swelling, and induration) for the respective event and “none” otherwise. The occurrence of at least one solicited adverse event (i.e., none versus any) will be summarized by category (i.e., local, systemic,

any), by vaccine group, by vaccination (after each vaccination and after any vaccination) and by time interval.

Medications to treat or prevent pain or fever will be summarized by frequencies and percentages of subjects reporting use of the medications by interval (30 min, 6h - day 3, day 4 - 7, 6h - day 7).

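### The Level 4 count of solicited-reaction days gives missing diary days zero, so a subject who stops reporting while the reaction is present enters the table as an exact, unmarked count that is really a minimum

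*SAP*

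**What the plan says.** Section 13.2 lists five levels of summary for solicited adverse events. The fourth is announced as "Duration of solicited adverse events". When it is defined, its heading changes to a number of days: "The number of days with the adverse event is defined irrespective of severity". A day counts if the reaction is at least mild, or at least 25 mm for erythema, induration and swelling. The one extension is "If a solicited adverse event continues beyond day 7 the period after day 7 is added". The example that follows is introduced as showing how duration is calculated, while its table title and last column again refer to days.

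On gaps in the diary the rule is "Missing values (‘Missing’) are not taken into consideration". A note under Level 2 treats a not-done entry like a missing one, and section 8.2.1 rules out imputation of safety data. The output is a frequency distribution of the counts by vaccine group, vaccination number and event. The SAP gives no category for incomplete counts, no minimum number of observed days and no sensitivity summary.

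Three rows of Table 13.2-3 matter here (6 hours, days 2 to 7, then the count):

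- first row: "None Severe Moderate None None None None 2"
- second row: "Mild None None Moderate Moderate Moderate Missing 4"
- fifth row: "None Mild Mild Missing Missing Missing Missing 2"

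**The concern.** The first and fifth rows both score 2, but they carry different information. The first subject had a complete diary and reported no reaction on days 4 to 7. The fifth subject had the reaction at the last entry and then nothing more was recorded. The first value is known; the fifth is a lower bound. The second row is a lower bound as well. In the planned table the three look alike.

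Reactogenicity serves the primary safety objective, which is safety compared with placebo. A reader of the Level 4 table will compare dosages and adjuvants on how many days reactions lasted. If subjects in some groups are more likely to stop the diary during a reaction, those groups' counts will be understated more than the others', and nothing in that table will show it.

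**Working it through.** **Inputs**, all from SAP section 13.2, Level 4 and Table 13.2-3: seven diary time points (6 hours, days 2 to 7); a positive entry counts 1; None, Missing and Not done count 0; known days after day 7 are added.

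**Formula.** Count = number of positive entries + known days after day 7.

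**Reproducing the SAP's column.**

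| Row | Positive entries | Days after day 7 | Count | SAP |
|---|---|---|---|---|
| 1 | 2 (days 2, 3) | 0 | 2 | 2 |
| 2 | 4 (6 h, days 4, 5, 6) | 0 | 4 | 4 |
| 3 | 6 (6 h, days 2, 4, 5, 6, 7) | 5 | 11 | 11 |
| 4 | 0 | 0 | 0 | 0 |
| 5 | 2 (days 2, 3) | 0 | 2 | 2 |
| 6 | 3 (6 h, days 3, 7) | 1 | 4 | 4 |

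All six match when a missing day adds 0. Numerically this is the same as recording None on that day.

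**Range allowed by the missing entries.** Lower limit = the count above. Upper limit = count + number of missing entries.

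| Row | Missing or not done | Last entry made | Range, diary week |
|---|---|---|---|
| 2 | 1 | Moderate | 4 to 4 + 1 = 5 |
| 4 | 1 | None | 0 to 0 + 1 = 1 |
| 5 | 4 | Mild | 2 to 2 + 4 = 6 |

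Rows 1, 3 and 6 have no missing entries and do not move. Because a missing day can add 0 or 1 but never subtract, the planned count is always at the bottom of its range. Row 5 rests on 7 − 4 = 3 observed time points. Rows 2 and 5 are the two in which the reaction was present at the last entry. Row 4 was negative at its last entry, so it is a weaker case.

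**The rule for reactions after day 7.** The SAP illustrates it only with rows 3 and 6, where day 7 was observed and positive. If row 2 were later reported as continuing to day 12, the stated rule would give 4 + 5 = 9. Day 7 would still be lost, although the reaction was reported as continuing past it. Counting day 7 gives 10.

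**Weight of one subject.** With about 24 subjects per group (section 4.1), and all of them in the denominator, one subject is 1/24 = 4.2% of the distribution. Each affected subject may place that share in too low a category.

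**The case against.** The strongest defence is that Level 4 is defined as a count of days and not as the length of an episode. The heading, the definition and the table column say so, and the example adds non-consecutive days across reaction-free ones (rows 2, 3 and 6). Read as days on which the reaction was reported, 2 and 4 are exact. This stands as a description of the arithmetic. It does not remove the problem, because the list of levels and the sentence introducing the example call the measure duration, and the number of days with the reaction in row 5 is still 2 to 6.

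There are also partial safeguards. Reminder calls are made 2 and 4 days after each dose, diaries are reviewed at the next visit, and interviews follow at 14 and 21 days. Section 13.1.1 tabulates valid data by group and time point, so uneven reporting would be visible there. Reactions known to continue past day 7 gain the later days. These steps limit the harm. None restores missing days within the week or marks the counts affected.

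Four stronger readings are tempting, and the SAP does not support them:

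- *The SAP records these reactions as completed.* It does not say so; it leaves them unmarked.
- *Level 4 contradicts the denominator rule.* Section 13.2 says that subjects without plausible data "will be removed from the denominator to prevent a downward bias (towards zero"). That covers subjects with no plausible observation in the interval. Partly observed diaries stay in throughout, so Level 4 does not reverse a stated rule. The general aim of avoiding bias towards zero is simply not carried into partly missing diaries.
- *The example measures the effect.* Two of its five subjects with an event (40%) are cut off while positive, and their mean would rise from 23/5 = 4.6 to 28/5 = 5.6 (22%) if the trailing missing days were positive. But the six subjects are invented to illustrate coding, and a mean is not a planned output.
- *Cut-off reactions look shortest, most of all in the most reactogenic groups.* Row 2 scores 4, equal to the fully observed row 6 and above row 1. No figure on reaction-related dropout or diary loss is given.

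**Conclusion.** The point holds in a limited form. When the last diary entry is positive and all later days through day 7 are missing, Level 4 enters a minimum as if it were exact, and the table cannot separate it from a fully observed reaction. Within the diary week the error runs in one direction only: up to 1 day for row 2 and up to 4 days for row 5 of the SAP's example.

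The size in the trial is unknown, because it depends on diary completion, which the SAP does not give. Loss that differs between groups is a possibility and not a finding. The summary is descriptive and no between-group test is specified for it, so this is a minor improvement. It is worth making because the table informs the primary safety objective, groups are small, and the remedy needs no new data.

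**What to change.** Keep the no-imputation rule for the main table and make these changes to Level 4:

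1. State that when the last non-missing diary entry for an event is positive, and every later diary day through day 7 is missing or not done, the count is reported as a minimum (at least x days) in a separate incomplete category. Give the number of such subjects by vaccine group and vaccination.
2. Mark the second and fifth rows of Table 13.2-3 as at least 4 and at least 2 days.
3. Add a sensitivity summary that counts the trailing missing days as event days (5 and 6 for those rows), named as an exception to section 8.2.1.
4. If a later report shows that the event continued past day 7, add the days after day 7 as already planned, and state that the missing days between the last positive entry and day 7 count as event days. The measure allows gaps, so this convention has to be written down; an instruction only to use the end date would leave it open.
5. Use one label, number of days, in the list of levels, the heading, the example and the output.

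The cost is a few sentences of SAP text, one extra category in a descriptive table and one short sensitivity summary.

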13.3 Unsolicited Adverse Events

The analysis will use unsolicited adverse event data from all reporting sources combined.

All the unsolicited AEs occurring during the study, judged either as probably related, possibly related, or not related to vaccination by the investigator, will be recorded. The original verbatim terms used by investigators to identify AEs in the CRFs will be mapped to preferred terms using the MedDRA dictionary. The unsolicited AEs will then be grouped by MedDRA preferred terms into frequency tables according to SOC.

All AEs will be summarized by vaccine group, according to SOC and PT within SOC. When an unsolicited AE occurs more than once for a subject, the maximal severity and strongest relationship to the vaccine group will be counted.

Only vaccine-emergent AEs will be analyzed, i.e., excluding those after a subject has given informed consent but before vaccination. The selection of unsolicited adverse events and the assignment to time intervals will be done by day of onset and not by days ongoing/persisting.

The summaries will be presented by period of onset and will include frequency distributions of the different adverse events:

- Vaccination 1 AEs, Onset between day 1 and day 28.
- Vaccination 2 AEs, Onset between day 29 and day 57.
- After either vaccination, Onset between day 1 and day 57
- Onset after day 57 through study end.
- At any time during the study, Onset after vaccination 1 on day 1

The analysis of unsolicited adverse events comprises the following categories:

- Any unsolicited adverse event.
- Possibly or probably related unsolicited adverse events.
- Unsolicited adverse events leading to death.

- Serious adverse events.
- Possibly or probably related serious adverse event.
- Unsolicited adverse events leading to premature withdrawal from study.
- Unsolicited adverse events leading to dose reduction, interruption or delay in study vaccination.
- Unsolicited adverse events leading to hospitalization.
- Unsolicited adverse events leading to new onset of chronic disease.
- Unsolicited adverse events of special interest.
- Medically attended adverse events.

Solicited adverse events continuing beyond day 7 will be coded by MedDRA and combined with the respective unsolicited adverse events.

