3. STUDY DESIGN

This is a Phase 1, randomized, observer blind, placebo-controlled, dosage-escalation, single center study, enrolling healthy adults. In total, approximately 288 healthy non-pregnant female and male adults (18 to 45 years of age) will be enrolled in the study in the ratio of 3:1. There is a higher ratio of female to male subjects because the RSV F subunit vaccine is ultimately intended for use in pregnant women. Men are still being included in this study because the vaccine may also be tested in the future in elderly subjects.

Approximately 288 healthy subjects will be enrolled (1:1:1) in a stepwise dosage-escalation manner in to one of three cohorts (cohort 1: low dosage of RSV F subunit vaccine [45 µg], cohort 2: middle dosage of RSV F subunit vaccine [90 µg], and cohort 3: high dosage of RSV F subunit vaccine [135 µg]). Cohort 1 will be enrolled first, followed by cohort 2, and finally cohort 3. Within each cohort subjects will be randomly allocated (1:1:1:1) to receive vaccine with no adjuvant, vaccine with aluminum hydroxide, vaccine with MF59, or saline placebo, as outlined in [Table 4-1](#). All subjects will receive two doses of a 0.5 mL intramuscular injection of the vaccine, with adjuvant (aluminum hydroxide [1 mg] or MF59 [0.25 mL; 9.75 mg squalene and surfactants]), the vaccine without adjuvant, or saline placebo. There will be approximately 24 subjects in each active treatment group and 24 placebo subjects per cohort) ([Table 4-1](#)).

The schedule of time and events, including whether a visit is a telephone call or a clinic visit is displayed in [Table 3-1](#).

Table 3-1: Times and Events Table

Study Period	Screen	Vaccine Dose #1 & Safety Follow-up				Vaccine Dose #2 & Safety Follow-up					Post-vaccination Follow-up				
		Clinic Visit	Clinic Visit	Reminder Call	Clinic Visit	Phone Call	Clinic Visit	Reminder Call	Clinic Visit	Phone Call	Clinic Visit	Clinic Visit	Clinic Visit	Clinic Visit	Clinic Visit
Study Day	-28 to -3	1	3, 5	8	15, 22	29	31, 33	36	43, 50	57	85	113	181	209	271, 366, 394
Days post 1 st dose		0	2, 4	7	14, 21	28	30, 32	35	42, 49	56					
Days post 2 nd dose						0	2, 4	7	14, 21	28	56				
Study Visit Window (min-max) in Days (d)	n/a	n/a	-1/+1	-1/+4 d	-1/+1	+14 d	-1/+1	-3/+3 d	-1/+1	-7/+7 d	-7/+7 d	-7/+7 d	-7/+7 d	-14/+14 d	-7/+7 d
Visit Number	Screening	1		2	3, 4	5		6	7, 8	9	10	11	12	13	14, 15, 16
Informed Consent	X														
Medical History	X														
Physical Exam ^a	X	X ^b		X		X ^b		X		X	X	X	X	X	

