- n. Safety data will be collected for 28 days following each vaccination. At 14 and 21 days after each dose, subjects will be interviewed by site staff using a scripted interview for collection of safety data. These safety data will be transcribed on source documents by the site staff performing the interviews.
- o. All medically attended AEs that lead to an unscheduled visit to a healthcare practitioner and/or a visit to the emergency department or its equivalent will be collected for 28 days following signing of the informed consent. SAEs, NOCDs and AEs leading to study or vaccine withdrawal will be collected through 1 year after receipt of the second dose. Please see protocol [section 6.6](#) for greater detail regarding methods for SAE and AEs leading to study or vaccine withdrawal collection.
- p. Adverse events of special interest (AESIs) will also be documented in all study subjects for the duration of the study. Monitoring for AESIs will be extended through 1 year after receipt of the second dose and will be accomplished at clinic visits or by a telephone follow-up call. A tabulation of all AESIs, categorized by MedDRA preferred terms and assessed relationship to study vaccine will be submitted as an addendum to the Clinical Study Report (CSR) if not included in the CSR.
- q. Collect concomitant medications and vaccination history according to the study procedures outlined in protocol [section 3.2.5](#) and [5.4](#).
- r. Any subject who terminates the study after receipt of vaccine (prior to Visit 9) is recommended to undergo study-related procedures required at Visit 9. For subjects who terminate after Visit 9, a telephone contact to assess for SAEs/AEs and associated concomitant medications is required.

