7.6 Safety Set

Solicited Safety Set

All subjects in the Exposed Set with any solicited adverse event data and/or indicators of solicited adverse events (e.g., use of analgesics/antipyretics).

For the by vaccination tabulations, solicited safety sets will be defined as follows:

- Solicited safety set #1 for post-injection reactions after the first dose (SOL 1)
- Solicited safety set #2 for post-injection reactions after the second dose (SOL 2)

Unsolicited Safety Set

All subjects in the Exposed Set with unsolicited adverse event (AE) data.

In this respect, a confirmation of no AE is considered as adverse event data; hence subject is to be included.

Five Unsolicited Safety Sets will be defined:

- Unsolicited Safety Set 1: from the day of dose 1 to before dose 2 at Visit 5 (UNSOL 1-28)
- Unsolicited Safety Set 2: from the day of dose 2 at Visit 5 to the day of Visit 9 (UNSOL 29-57)
- Unsolicited Safety Set 3: From the day of dose 1 to the day of Visit 9 (UNSOL 1-57)
- Unsolicited Safety Set 4: The day of Visit 9 to study completion (UNSOL 58-394)
- Unsolicited Safety Set 5: Day 1 – Day 394 (UNSOL 1-394)

Overall Safety Set

All subjects who are in the solicited safety set and/or in the unsolicited safety set.

Subjects providing only 30 minutes post-vaccination safety data will be reported separately in a 30 minute post-vaccination safety analysis and excluded from all other safety analysis.

In case of vaccination error, subjects will be analyzed as “treated” (i.e., according to the vaccine a subject receives, rather than the vaccine to which the subject is randomized).

If a subject is unblinded during the study, he/she will be included in all the safety sets.

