8.2 Handling of Dropouts, Missing Data

8.2.1 Safety Data

For unsolicited adverse events, the entire study period will be divided into the following intervals: “day 1 – day 28, day 29 – day 57, day 58 – day 394”.

For solicited adverse events, the solicited study period “30 min - day 7” will be divided into: “30 min, 6h - day 3, day 4 - day 7, and 6h - day 7”.

No imputation methods will be used to address missing values.

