8.7 Derived and Computed Variables

Demographics

Age will be calculated in years using the following formula:

$$(\text{Date of Visit 1} - \text{Date of Birth} + 1) / 365.25$$

Body Mass Index (kg/m²) will be calculated using the following formula:

$$\text{Weight (kg)} / \text{Height}^2 (\text{m}^2)$$

Immunogenicity

Values below the limit of quantification (LLQ = 1:100, recorded as “< LLQ”) will be set to half that limit (i.e., LLQ/2 = 1:50).

Geometric Mean Titer

The GMT will be calculated using the following formula:

$$10^{\left\{ \frac{\sum_{i=1}^n \log_{10}(t_i)}{n} \right\}}$$

where t_1, t_2, \dots, t_n are n observed immunogenicity titers/concentrations.

Ratio greater or equal to a given threshold is defined for non-missing values as:

= 1, if the concentration relative to pre-vaccination is superior or equal to the given fold-rise threshold

= 0, otherwise

Value of 4 fold-rise will be used.

Duration in the Study

Duration in the study is defined in days as:

Last visit date (visit x)^a – Enrollment date (visit 1) + 1

^aor premature discontinuation date (in case of withdrawal from the study)

The duration is missing if one of the dates is missing or incomplete.

Duration in the study after vaccination 1 is defined in days as:

Date of vaccination 2 (visit 5) – Date of vaccination 1 (visit 2)

Duration in the study after vaccination 2 is defined in days as:

Date of vaccination 2 follow-up (visit 9) – Date of vaccination 2 (visit 5)

Solicited Adverse Events

For details see [section 13.2](#).

Unsolicited Adverse Events

All adverse events will be characterized according to the date of occurrence related to the vaccination phase as follows:

- **Emergence before vaccination phase:** start date before the first date of injection of study vaccine.
- **Emergence during vaccination phase:** start date on or after the first date of injection of study vaccine or, adverse event increase in severity including to “serious” adverse event.

If start date is equal to the first date of injection then “timing” variable (“On injection day, before injection”/“On injection day, after injection”) will be used to define whether the adverse event occur before or after the injection.

If there are several vaccinations, the adverse event will be associated with the most recent vaccination.

If an adverse event start date is missing or unknown, the adverse event will be considered as emergent.

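### Unsolicited AE periods are cut at nominal study days in SAP 13.3 and 8.2.1 but at actual dose 2 and Visit 9 dates in 7.6 and 8.7, and Table 3-1 footnotes n and o conflict on medically attended AEs

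*SAP*

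**What the plan says.** The file holds three successive versions of the SAP. Everything here refers to the last one.

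- **Section 13.3** sets the reporting periods: "Vaccination 1 AEs, Onset between day 1 and day 28", then "Vaccination 2 AEs, Onset between day 29 and day 57", then days 1 to 57 combined, onset after day 57, and the whole study. It adds that "assignment to time intervals will be done by day of onset and not by days ongoing/persisting".
- **Section 8.2.1** divides the study in the same way: "day 1 – day 28, day 29 – day 57, day 58 – day 394".
- **Table 3-1**, in the row "Study Visit Window (min-max) in Days (d", gives +14 d for Visit 5 (nominal Day 29, dose 2) and -7/+7 d for Visit 9 (nominal Day 57).
- **Section 7.6** defines the unsolicited safety sets by events in the subject's own calendar. Set 1 runs from dose 1 until just before dose 2. The next is "Unsolicited Safety Set 2: from the day of dose 2 at Visit 5 to the day of Visit 9 (UNSOL 29-57"). Set 4 begins on the day of Visit 9, the day on which Sets 2 and 3 end, although its label is 58-394.
- **Section 8.7** states: "If there are several vaccinations, the adverse event will be associated with the most recent vaccination". Its variable for onset before or after injection on the same day is specified only for the first injection date.
- **Table 3-1, footnotes n and o.** Footnote n collects safety data for 28 days after each vaccination. Footnote o says that medically attended AEs "will be collected for 28 days following signing of the informed consent". Section 13.3 lists medically attended AEs as a category without limiting it to any period.

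**The concern.** The SAP holds two rules for one set of tables. The populations and the attribution of an event to a dose follow actual dates; the tables follow nominal days. They agree only when dose 2 is given on Day 29 and Visit 9 takes place on Day 57. Two programmers could each follow the SAP and produce different per-dose tables, and the numerator and denominator of one table could come from different rules.

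Safety is a primary objective of this first-in-human, two-dose study, and reactions by dose are a main output. With about 24 subjects per group, moving one subject between periods changes a group's rate by 1/24, about 4 percentage points.

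The medically attended AE point is separate. If the collection window closes before dose 2, a zero in a later period says nothing about safety, yet 13.3 does not prevent such a table.

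**Working it through.** The SAP states no figure to reproduce, so the check is study-day arithmetic. Day 1 is 0 days after dose 1. As a check, dose 2 on Day 29 plus 28 days is Day 57, which agrees with Table 3-1.

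**1. Permitted dose 2 days.** Day 29 with a window of +14 d gives Days 29 to 43.

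**2. Literal use of the 13.3 cuts.** Let *d* be the day of dose 2. The Vaccination 2 period, Days 29 to 57, has 57 − 29 + 1 = 29 days. The post-dose-2 period (footnote n's 28 days plus the dose day) also has 29 days, from *d* to *d* + 28.

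- Vaccination 2 days that precede dose 2: *d* − 29.
- Post-dose-2 days that fall after day 57: (*d* + 28) − 57 = *d* − 29.

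| Dose 2 on | Vaccination 2 days before dose 2 | Share of 29 | Post-dose-2 period ends | Post-dose-2 days moved to follow-up |
|---|---|---|---|---|
| Day 29 | 0 | 0% | Day 57 | 0 |
| Day 36 | 7 | 24% | Day 64 | 7 |
| Day 43 | 14 | 48% | Day 71 | 14 (Days 58 to 71) |

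With the cuts tied to the actual dose 2 date, as in 7.6 and 8.7, the number of days before dose 2 in the second period is 0 for every *d*.

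**3. The Visit 9 boundary.** Even with dose 2 on Day 29, Visit 9 may fall on Days 50 to 64 (57 ± 7). Set 2 then ends up to 7 days before or after the table's Day 57 cut. This does not change the dose to which an event belongs, but the set and the table cover different days.

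**4. Shared and unsplit days.** Set 4 as worded shares the Visit 9 date with Sets 2 and 3. An event starting on the date of dose 2 has no stated rule for before or after injection, because 8.7 gives that rule for the first injection only.

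**5. Medically attended AEs under footnote o.** Consent is at screening, Day −28 to Day −3.

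- Consent on Day −28: collection ends on Day 1 (Day 0 if a Day 0 is counted).
- Consent on Day −3: collection ends on Day 26 (or Day 25).

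The window therefore always closes before Day 29, the earliest dose 2. Under footnote n both dose periods would be covered. Neither footnote covers every medically attended event with onset after day 57. An event starting more than 28 days after a dose would be captured only if it also fell in a long-term category, such as SAEs or new-onset chronic disease.

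**The case against.** The strongest reply is that the day ranges in 13.3 are shorthand. Section 7.6 attaches the tags 1-28 and 29-57 to sets that it defines by actual dates, and 8.7 ties each event to the latest dose given. Read together, 13.3 borrows those tags and no event is misassigned. That reading is open, so a reader should not infer that events will be credited to the wrong dose. But 13.3 does not say that its days are shorthand, and 8.2.1 repeats the nominal cuts, so the contradiction stands.

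Four further limits are fair:

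- **Size.** The 14 days (48%) is a per-subject maximum. Only a subject with an onset in the displaced days is affected, so it does not follow that results are wrong for every subject with a delayed dose 2. The whole-study table is untouched.
- **Comparison with placebo.** The same cuts apply to all arms of a randomised cohort. Bias between arms would need dose 2 delay to differ by arm, and the SAP gives no evidence on that.
- **Visit 9 day.** A reader might infer that events on that day are counted twice. The sets are populations of subjects, who may belong to several, and 13.3 and 8.2.1 start follow-up after day 57. The shared day is a loose definition, not proven double counting.
- **Medically attended AEs.** Section 13.3 lists periods and categories separately, so tabulating this category in all five periods is an inference. Table 3-1 also has all AEs assessed at later visits, and under footnote n events within 28 days of a dose would be captured. It is therefore not shown that these events would be missing. The conflict between the two footnotes remains.

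**Conclusion.** The concern holds as an internal contradiction. Sections 13.3 and 8.2.1 use nominal days, 7.6 and 8.7 use actual dates, and the permitted dose 2 window makes the difference matter. Under the literal reading of 13.3, the displacement runs from 0 days (dose 2 on Day 29) to 14 days each way (dose 2 on Day 43). This assumes that dosing stays within the Table 3-1 window and that post-dose-2 safety follow-up lasts 28 days from the actual dose, as in footnote n. The effect on reported rates cannot be sized, because the SAP does not give the spread of dose 2 dates. Under the shorthand reading the displacement before dose 2 is nil, and only the wording needs correction.

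Footnotes n and o give incompatible collection windows. Under o, collection of medically attended AEs ends by about Day 26 at the latest, so it cannot support a table for dose 2 or follow-up. The change should be made before the tables are programmed.

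**What to change.** 1. In 13.3 and 8.2.1, define the periods by actual dates, consistent with 7.6 and 8.7: dose 1 to before dose 2; dose 2 to Visit 9; the day after Visit 9 to study end. Keep the day ranges, if wanted, as labels stated to be nominal. State what closes a period for a subject with no dose 2 or no Visit 9.
2. In 7.6, start Set 4 on the day after Visit 9, so that it shares no day with Sets 2 and 3.
3. In 8.7, apply the before/after-injection timing variable to the dose 2 date as well as the first.
4. Reconcile footnotes n and o of Table 3-1, and limit the medically attended AE tables in 13.3 to the periods in which these events were collected.

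The cost is SAP wording and small changes to date derivations that 7.6 and 8.7 already require. No change to sample size or to the primary immunogenicity analysis follows from it.
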